2. SUMMARY OF KEY PROTOCOL INFORMATION

2.1. Changes to the Protocol Defined Statistical Analysis Plan

This study was terminated due to feasibility. Due to the low number of subjects involved, the analysis is modified and certain analysis won't be performed. Please refer to below section for more details.

[figure not shown]
2.2. Study Objective(s) and Endpoint(s)

Objectives	Endpoints
Primary	Primary

 To demonstrate the superiority of retosiban to prolong pregnancy compared with atosiban. 	
 Time to delivery from the start of IP administration until delivery, based on a records review.
Secondary	
Secondary
 
Key Secondary Endpoints
 
 Proportion of births prior to $37^{0/7}$ weeks' gestation – ascertain the GA at delivery based on a record review Proportion of births at term ($37^{0/7}$ to $41^{6/7}$ weeks' gestation) – ascertain the GA at delivery based on a record review Length of neonatal hospital stay – confirm duration (in days) of neonatal hospital admission from the medical records Proportion of neonates with any diagnosis from the neonatal morbidity and mortality composite determined up to 28 days after estimated date of delivery (EDD) (of $40^{0/7}$ weeks) 
Other Secondary Endpoints
 
 Proportion of neonates with any of the composite neonatal morbidity and mortality excluding Respiratory Distress Syndrome (RDS) Proportion of neonates with each individual component of the composite neonatal morbidity and mortality Neonatal admission to a specialized care unit and length of stay – confirm admission to neonatal intensive or

Objectives	Endpoints
	
specialized care unit from the medical records
 
 • Newborn hospital readmission and length of stay – confirm any neonatal hospital readmission following the birth hospitalization, the reason for admission, and the length of stay from the medical records • Proportion of births prior to $28^{0/7}$ weeks' gestation • Proportion of births prior to $32^{0/7}$ weeks' gestation • Proportion of births prior to $35^{0/7}$ weeks' gestation • Proportion of births ≤ 7 days from the first study treatment • Proportion of births ≤ 48 hours from the first study treatment • Proportion of births ≤ 24 hours from the first study treatment

2.3. Study Design

Overview of Key Study Design Features	
Design Features:	
 Phase III, randomized, double-blind, double-dummy, multicenter design Subjects are females, aged 18 to 45 years (Sweden) or aged 12 to 45 years (all other countries including UK, Germany, Italy, Israel, South Korea, Belgium, Mexico, Spain and Brazil), with an uncomplicated, singleton pregnancy and intact membranes in preterm labor between 24^{0/7} and 33^{6/7} weeks of gestation.
Dosing:	
 Retosiban treatment will be administered as a 6-mg IV loading dose over 5 minutes, followed by a 6-mg/hour continuous infusion over 48 hours. Atosiban will be given intravenously in 3 successive stages: an initial bolus dose of 6.75 mg using atosiban 6.75 mg/0.9 mL solution for injection, immediately followed by a continuous high dose infusion at 18 mg/hour for 3 hours, then a lower 6 mg/hour infusion for the remainder of the 48-hour treatment period using the atosiban 37.5 mg/5 mL concentrate for solution.
Treatment Assignment:	
 A total of 97 patients were blindly randomly assigned to retosiban or atosiban in a 1:1 ratio. Subjects were stratified by established progesterone treatment (Yes/No) and gestational age at randomization (24^{0/7} to 25^{6/7}, 26^{0/7} to 27^{6/7}, 28^{0/7} to 30^{6/7} and 31^{0/7} to 33^{6/7}). Subjects within each stratum will be randomly assigned in 1:1 ratio to receive either retosiban or atosiban using an IVRS in accordance with the randomization schedule.
Interim Analysis	
 The study was terminated before interim analysis due to feasibility. Details of the interim analysis were written in the IDMC RAP.

2.4. Statistical Hypotheses

The primary endpoint is prolongation of pregnancy as measured by time to delivery (days). The following are the null (H_0) and alternative (H_1) hypotheses for the primary endpoint in this study:

- H_0 : The prolongation of pregnancy as measured by time to delivery is equal between the women randomized to retosiban versus atosiban
- H_1 : The prolongation of pregnancy as measured by time to delivery is unequal between the women randomized to retosiban versus atosiban

The primary objective of the statistical analysis will be to test the null hypothesis in intent-to-treat (ITT) Population that there is no difference between retosiban and atosiban and the alternative hypothesis that there is a difference for the primary endpoint. The hypotheses will be tested at 5% level in a 2-sided test.

3. PLANNED ANALYSES

All planned analyses will be done using SAS version 9.2 or higher. The Analysis Data Model (ADaM) will be created per ADaM implementation guide version 1.1. Details on

derivation of variables will be specified in the specification document of ADaM. All analysis tables, listings and figures will be generated based on ADaM and/or Study Data Tabulation Model (SDTM).

3.1. Interim Analyses

No interim analysis was conducted.

3.2. Final Analyses

The final planned analyses will be performed after the completion of the following sequential steps:

1. All subjects have completed the study as defined in the protocol.
2. All required database cleaning activities have been completed and the final database release and database freeze has been declared by Data Management.
3. All criteria for unblinding the study have been met.
4. Randomization codes have been distributed.

4. ANALYSIS POPULATIONS

Population	Definition / Criteria	Analyses Evaluated
All Randomized	
 • Consists of all mothers randomly assigned to treatment regardless of whether they actually are treated. • Subjects will be presented by their planned randomized treatment 	
 • Subject Disposition
Randomized but not dosed	
 • Consists of all mothers that are randomized but fail to receive any study treatment. • Subjects will be presented by their planned randomized treatment. 	
 • Subject Disposition
Maternal Safety	
 • Mothers randomly assigned to treatment who have been exposed to study treatment. • Randomly assigned subjects will only be excluded if there is clear evidence the subject did not receive IP. • Subjects will be analyzed according to their actual treatment. Any subject who received both treatments (retosiban and atosiban) will be assigned to retosiban group for actual treatment. 	
 • Maternal and fetal safety
Neonatal Safety	
 • Consists of neonates whose mothers received randomized treatment. • Subjects are analyzed according to the actual treatment their mothers received. • Any subject who received both treatments (retosiban and atosiban) will be assigned to retosiban group for actual treatment. 	
 • Neonatal safety
Maternal ITT	
 • Consists of all mothers randomly assigned to treatment who have been exposed to study treatment irrespective of their compliance to the planned course of treatment. • Subjects who are randomly assigned but fail to receive any study treatment will be presented separately. 	
 • Maternal and fetal efficacy endpoints
Neonatal ITT	
 • Dataset comprises all neonates whose mothers are the randomized Subjects who have been exposed to study drug, i.e., mothers from the ITT Population. 	
 • Neonatal efficacy endpoints

NOTE :

- Please refer to Section 11.11 Appendix 11: List of Data Displays which details the population to be used for each display being generated.

4.1. Protocol Deviations

- Significant protocol deviations (including deviations related to study inclusion/exclusion criteria, study treatment, conduct of the trial, patient management or patient assessment) will be listed.
- Protocol deviations are tracked by the study team throughout the conduct of the study in accordance with the Protocol Deviation Management Plan (Reference).
 - Data will be reviewed prior to unblinding and freezing the database to ensure all significant protocol deviations and non-significant deviations which may lead to exclusion from the analysis are captured and categorised on the protocol deviations dataset.

5. GENERAL CONSIDERATIONS FOR DATA ANALYSES AND DATA HANDLING CONVENTIONS

5.1. Subgroups

5.1.1. Efficacy Analyses

The comparison of the treatment groups for the primary and selected secondary efficacy endpoints (i.e., prolongation of pregnancy, neonatal composite) will be analyzed by the following subgroups if applicable:

- GA at randomization with 4 categories: 24^{0/7} to 25^{6/7}, 26^{0/7} to 27^{6/7}, 28^{0/7} to 30^{6/7} and 31^{0/7} to 33^{6/7}
- Established progesterone group with categories “Yes” and “No”

In addition, for the primary efficacy endpoint, there are no per-protocol population defined, so additional subgroup analyses based on major protocol deviations or violation of PTL criteria (inclusion criteria #4) may be performed as appropriate. Also, additional subgroup analysis based on the status of spontaneous onset delivery will be performed.

5.1.2. Safety Analyses

Safety data will be summarized by the following subgroups if applicable:

- GA at randomization with 4 categories: 24^{0/7} to 25^{6/7}, 26^{0/7} to 27^{6/7}, 28^{0/7} to 30^{6/7} and 31^{0/7} to 33^{6/7}

Additional subgroup analyses may be performed as appropriate.

5.2. Multiplicity Adjustment

There will be no multiplicity adjustment due to early termination of the study.

No formal tests of hypothesis will be performed on safety data.

Table 1 provides an overview of appendices within the RAP for outlining general considerations for data analyses and data handling conventions.

Table 1 Overview of Appendices

Section	Component
11.1	Appendix 1: Protocol Deviation Definitions
11.2	Appendix 2: Time and Events
11.3	Appendix 3: Treatment States and Phases
11.4	Appendix 4: Data Display Standards & Handling Conventions
11.5	Appendix 5: Derived and Transformed Data
11.6	Appendix 6: Premature Withdrawals & Handling of Missing Data
11.7	Appendix 7: Primary and Sensitivity Analyses for Primary and Key Secondary Endpoints with Missing Data
11.8	Appendix 8: Values of Potential Clinical Importance
11.9	Appendix 9: Model Checking and Diagnostics for Statistical Analyses
11.10	Appendix 10: Abbreviations & Trade Marks
11.11	Appendix 11: List of Data Displays

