1. REPORTING & ANALYSIS PLAN SYNOPSIS

Overview	Key Elements of the RAP
Purpose	
 This Reporting and Analysis Plan (RAP) details all planned efficacy and safety analyses and outputs required for the final Clinical Study Report (CSR) of study 200721.
Protocol	
 This RAP is based on the original protocol (Dated: 14-May-2014), country-specific amendment 02 (France; dated 29-Jan-2015, country-specific amendment 02 (United Kingdom; dated 29-Jan-2015) and country-specific amendment 03 (Sweden; dated 04-Feb-2015), protocol amendment 04 (Dated: 22-Aug-2016), and protocol amendment 05 (Dated: 21-Dec-2016) for study GSK200721 [GlaxoSmithKline Document Numbers: 2014N194185_00, 2014N194185_01, 2014N194185_02, 2014N194185_03, 2014N194185_04 and 2014N194185_05].
Primary Objective	
 Demonstrate the superiority of retosiban to prolong pregnancy compared with atosiban.
Primary Endpoint	
 Time to delivery (in days) from the start of investigational product (IP) administration until delivery, based on a records review.
Study Design	
 Phase III, randomized, double-blind, double-dummy, multicenter study to investigate efficacy and safety of 6-mg IV loading dose of retosiban over 5 minutes, followed by a 6-mg/hour continuous infusion over 48 hours in women aged 18 to 45 years (Sweden) or aged 12 to 45 years (all other countries) with an uncomplicated singleton pregnancy in preterm labor with intact membranes between 24^{0/7} and 33^{6/7} weeks' gestation. The study was terminated due to feasibility reason. The study enrolled 97 patients and patients were randomly assigned to one active arm (retosiban) and one active control arm (atosiban).
Planned Analyses	
 Interim analyses are described in Independent Data Monitoring Committee (IDMC) RAP. Final efficacy and safety analyses are detailed within Section 3.2. All decisions regarding final analyses, as defined in this RAP document, will be made prior to Database Freeze (unblinding) of the study data.
Primary Analysis Population	
 The Maternal and Neonatal Safety Analysis Population will be used to evaluate safety. The Intent-to-treat (ITT) Maternal and Neonatal Analysis Populations will be used to evaluate efficacy.

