8.1.2. Planned Key Secondary Efficacy Statistical Analyses

Key Secondary Efficacy Statistical Analysis	
Endpoint	
	
 • Proportion of births prior to $37^{0/7}$ weeks' gestation • Proportion of births at term ($\geq 37^{0/7}$ weeks' gestation) • Length of neonatal hospital stay • Proportion of neonates with any diagnosis from the neonatal morbidity and mortality composite determined up to 28 days after EDD (of $40^{0/7}$ weeks) (details for each composite are provided in Section 11.5.4.)

To preserve the overall type I error rate, the key secondary analysis will be performed if and only if the null hypothesis of the primary endpoint is rejected. In addition, a sequential testing method will be used to adjust for multiplicity of the key secondary endpoints such that the type I error rate will be maintained at 5%. The sequential testing examines the hypothesis testing in a pre-specified order, i.e., the testing of the second secondary endpoint will be performed only if the first secondary endpoint is significant at 5%, and testing of the third secondary endpoint will be performed only if the first and second endpoints are significant at 5%.
 
Order of sequential testing is
 
 1) Length of neonatal hospital stay 2) Proportion of births prior to $37^{0/7}$ weeks' gestation and Proportion of births at term 3) Neonate composite outcome 	
Model Specification	

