9. DEVIATION OF PLANNED ANALYSES FROM PROTOCOL

No changes will be made to the planned analyses after the breaking of the study blind; however, due to the early termination of the study and the resultant low number of subjects enrolled in the study, not all originally planned data analyses, as outlined in the protocol, will be performed.

The following changes will be made to the planned analyses from the protocol:

- The following subgroup analyses for the primary and key secondary endpoints will not be performed.
 - Magnesium sulfate use
 - Putative tocolytic use following IP discontinuation
- Other exploratory covariate analyses will not be performed to examine the relationship between the treatment response and potential covariates including baseline fFN value, subclinical intrauterine infection, and other concomitant medications.
- Maternal and neonatal health outcomes will not be analysed but will be presented in data listings and analysis by subgroups will not be explored.

- Data will not be presented for neonatal ambulatory surgery as part of neonatal health care resource use results.
- No formal interim analyses will be performed.
- The PK data will be not analysed but will be listed for plasma, cord blood and blood milk samples.
- No analysis for retosiban clearance and volume of distribution and the effect of covariates on these parameters will be performed.
- Newborn hospital readmission and length of stay will not be analysed but will be listed.
- Incidence of treatment-limiting toxicities including both clinical and laboratory etiology causing subject to discontinue study treatment will not be analysed.
- No analysis for Edinburgh Postnatal Depression Scale and EQ-5D-5L will be performed.
- No analysis using per-protocol (PP) population will be performed.

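### SAP 5.2 drops multiplicity adjustment, but SAP 8.1.2 keeps the gate on the primary, the fixed testing order and the 5% error claim; term birth within that order has two definitions

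*SAP*

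**What the plan says.** SAP Section 5.2 reads: "There will be no multiplicity adjustment due to early termination of the study".

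SAP Section 8.1.2 keeps the full confirmatory structure. First there is a gate: "the key secondary analysis will be performed if and only if the null hypothesis of the primary endpoint is rejected". Then there is a fixed sequence, in which "testing of the third secondary endpoint will be performed only if the first and second endpoints are significant at 5" per cent, with the type I error said to stay at 5%. The order is length of neonatal hospital stay, then a step written as "Proportion of births prior to $37^{0/7}$ weeks' gestation and Proportion of births at term", then the neonatal composite.

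The protocol (Sections 8.1 and 8.3.5.1.2) requires the gate and the sequence and leaves the order to the analysis plan.

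SAP Section 2.1 says "Due to the low number of subjects involved, the analysis is modified". SAP Section 9 introduces its list with "The following changes will be made to the planned analyses from the protocol". Neither the loss of the sequential method nor a change in the term-birth definition is on that list. Section 9 also says "No changes will be made to the planned analyses after the breaking of the study blind".

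Term birth is 37 0/7 weeks or later, with no upper limit, in the SAP 8.1.2 endpoint list and the SAP 11.5.4 derivation. It is 37 0/7 to 41 6/7 weeks in the SAP synopsis, SAP 2.2, SAP Table 4, the SAP 8.1.2 model specification, and protocol 6.2.4 and 8.3.5.1.2.

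**The concern.** The two SAP sections give opposite instructions on two matters: whether the key secondary tests are run at all when the primary is not rejected, and whether their p-values are confirmatory or nominal.

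Under 5.2, the 5% statement left in 8.1.2 is untrue, and someone working from 8.1.2 could present unadjusted p-values as error-controlled. Under 8.1.2, a non-significant primary would remove analyses that the post-termination display list still includes. Because Section 9 rules out changes once the blind is broken, a choice made after that point would be open to the charge that the results drove it.

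The two term-birth definitions sit inside the same sequence. Under one, step 2 is a single test stated twice. Under the other, it is two tests, and the plan does not say whether one of them may be claimed alone.

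**Working it through.** **Inputs from the documents.** Two-sided 5% per test (protocol 8.3.3.2 for secondary endpoints). Four named key secondary endpoints in three steps (SAP 8.1.2). "The study enrolled 97 patients" (SAP synopsis).

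**Assumptions.** The documents give no correlations between endpoints and no share of births at 42 0/7 weeks or later. Common correlations of 0, 0.5 and 0.8, and late-birth shares of 0%, 1% and 2%, are used to show a range.

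**1. The plan's 5%.** A strict single order was simulated (primary, stay, preterm birth, term birth, composite) with 2,000,000 replicates. It was run with all nulls true and with the first one to four hypotheses false. The familywise error was 0.0499 to 0.0503. The 5% in 8.1.2 is therefore right if the sequence is followed as one strict order.

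**2. No adjustment, term birth 37 0/7 weeks or later.** Term birth is then the exact complement of birth before 37 0/7 weeks, so there are three distinct tests.
- Independent: 1 − 0.95³ = 1 − 0.8574 = 14.3%.
- Equally correlated normal statistics, by numerical integration: 12.5% at 0.5 and 9.8% at 0.8.

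**3. No adjustment, term birth 37 0/7 to 41 6/7 weeks.** There are now four tests.
- Treated as equally correlated: 1 − 0.95⁴ = 1 − 0.8145 = 18.5% if independent, 15.6% at 0.5 and 11.4% at 0.8. These overstate the case, because preterm and term birth are nearly complementary.
- A more realistic case assumes 50% of births before 37 weeks and 2% at 42 0/7 or later, leaving 48% at term. The two indicators correlate at −(0.50 × 0.48)/√(0.50 × 0.50 × 0.48 × 0.52) = −0.96.
- The term-birth statistic is set at −0.96 times the preterm statistic plus independent noise, so its correlation with the other two is −0.96 times the common value. The results are 15.5%, 13.6% and 10.7% at common correlations of 0, 0.5 and 0.8.

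**4. Passing step 2 if the sequence is kept.** With the bounded definition, requiring both endpoints keeps the step at or below 5%. If either alone sufficed, the error for the pair would be 5.7%, 6.5% or 7.0% at absolute correlations of 0.99, 0.95 or 0.90. The natural reading of 8.1.2 is that both are needed, but it does not say so.

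**5. Births affected by the definition.** Only births at 42 0/7 weeks or later move. Of 97 women: 97 × 0.00 = 0; 97 × 0.01 = 0.97, about 1; 97 × 0.02 = 1.94, about 2. With none, the definitions coincide.

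**The case against.** The strongest reply is that the SAP shows which rule is meant. Section 5.2 is the only multiplicity text that gives early termination as its reason. Section 2.1 announces modifications and points the reader further down the document, where 5.2 lies. Section 8.1.2 calls for key secondary p-values without repeating the condition in its results presentation. Appendix 11 limits output to the displays kept after termination, and these include Tables 2.101, 2.181 and 2.301 with no condition on the primary. The gate and sequence in 8.1.2 follow the protocol closely and look carried over.

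This stands as evidence that 5.2 is the intended rule. It does not settle the matter. No passage says 5.2 prevails, and the 5% claim remains in the text. Nor is 8.1.2 purely inherited: it supplies the testing order that the protocol had left open.

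It is also fair to say that the stakes are limited. The trial stopped for feasibility at 97 women against about 330 planned, the primary is untouched, and the term-birth difference may affect no one. The 18.5% figure should not carry the argument. All of that bears on weight, not on whether the text needs correcting. The open-ended definition also appears in the heading of SAP 11.7.3 and in the term-delivery category of SAP 8.2.4.2, so a clean-up should cover those too.

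**Conclusion.** The concern holds: the SAP contradicts itself on multiplicity. If 5.2 governs, the familywise error over the key secondaries is about 10% to 14% with term birth open-ended, or about 11% to 15.5% with the bounded definition and the assumed birth shares. The text in 8.1.2 says 5%. If 8.1.2 governs, 5.2 is wrong, and the key secondary analyses depend on the primary result. Either way Section 9 is incomplete.

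The ranges assume all nulls true, two-sided 5% tests and common correlations between 0 and 0.8. The contradiction itself needs no assumption. The term-birth mismatch is real but minor, at 0 to 2 births under assumed rates of 0% to 2%. This should be fixed before unblinding; it does not threaten the primary analysis.

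**What to change.** State one rule before the blind is broken.

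**Preferred.** Take the gate, the sequence and the 5% statement out of SAP 8.1.2. Label all key secondary p-values nominal and descriptive, with no confirmatory claim, and add the dropped sequential method to the Section 9 list. The multiplicity change needs SAP wording only. The price is that no secondary result can be claimed as confirmatory, which 5.2 already implies.

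**Alternative.** Delete the first sentence of 5.2 and keep the sequence. Reword the gate to say what is shown when the primary is not rejected, for example estimates with 95% confidence intervals and no p-values. This also needs a small change to the displays. Step 2 then needs a single endpoint under the open-ended definition. Under the bounded one it needs two separately ordered steps, or term birth reported descriptively.

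**In either case** use one definition of term birth throughout the SAP and list any departure from the protocol in Section 9. Choosing 37 0/7 to 41 6/7 weeks means a minor edit to the 11.5.4 derivation and matching edits to the 8.1.2 endpoint list and the 11.7.3 heading. Choosing 37 0/7 weeks or later means correcting the synopsis, Section 2.2, Table 4 and the 8.1.2 model text, with a Section 9 entry.
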